2.1 Data analysis general information

The data will be analyzed by Novartis and/or a designated clinical research organization (CRO). Any data analysis carried out independently by the investigator should be submitted to Novartis before publication or presentation.

Statistical analysis of all data will be performed using SAS[®] statistical software (SAS Institute, Cary, NC, USA) version 9.4 or higher.

General descriptive statistical rules

Categorical data will be presented as frequencies and percentages. In general, missing values are not considered for calculation of percentages (i.e., adjusted percentages are calculated) if not otherwise specified.

For continuous data, the number of non-missing observations, mean, standard deviation, median, minimum, and maximum will be presented.

Unless otherwise stated, summary tables/figures/listings (TFLs) will be presented for each treatment arm in the respective analysis set.

General information on treatment arm handling, decimal places and other output-related information will be specified in TFL shells accompanying this analysis plan.

2.1.1 General definitions

Study treatment

Novartis will supply the investigational medication listed below:

- 2 × secukinumab 150 mg PFS, s.c.
- 2 × matching placebo 0 mg PFS, s.c.

Eligible patients will be randomized in a 1:1 ratio to one of the double-blinded treatment arms.

Treatment groups

- Randomized treatment:
 - AIN457 300 mg: All patients randomized to secukinumab.
 - Placebo: Patients randomized to placebo.
- Treatment sequence:
 - **AIN457 – AIN457:** Patients randomized to secukinumab and switched to open-label secukinumab treatment in follow-up period (“AIN457 non-responder”).
 - **Placebo – AIN457:** Patients randomized to placebo and switched to open-label secukinumab treatment in follow-up period (“placebo non-responder”).

Frequency of administration

Baseline to Week 16 (Double-blind):

- Secukinumab (300 mg): Baseline, Week 1, Week 2, Week 3, Week 4, Week 8 and Week 12
- Placebo: Baseline, Week 1, Week 2, Week 3, Week 4, Week 8 and Week 12

Week 16 to end of study (EOS) (Open-label):

- Non-responders at Week 16: Secukinumab (300 mg) at Week 16, Week 17, Week 18, Week 19, Week 20, Week 24 and Week 28;
- Responders at Week 16 who relapse thereafter: Secukinumab (300 mg) at time of relapse, then 1, 2, 3, 4, 8 and 12 weeks from time of relapse.

Stratification factor

Patients will be stratified according to current smoking status (up to 20% smokers per arm), since smoking has a well-known impact on treatment efficacy in TED.

2.1.1.1 Study dates

Screening/ Baseline

Screening period will occur for a maximum of 6 weeks (Day -42 to -1). Baseline is defined as the day with the last assessment on or before first dose. At Baseline all eligible patients will be randomized via Interactive Response Technology (IRT) to one of the treatment arms.

Randomization (enrollment) date in DBTP

Randomization (enrollment) date in double-blind treatment period (DBTP) is the date on which a subject is assigned to one of the treatments through IRT in DBTP.

First IP dose date

The first investigational product (IP) dose date is the date on which a subject is administered the first dose of IP following randomization.

Last IP dose date

The last IP dose date for each subject is defined as the latest date IP is administered (including study medication in the open-label retreatment phase).

Subject-level end of treatment (EOT) date

The EOT date (including the open-label retreatment phase) for each subject is defined as the minimum of (last dose date + 84 days) and EOS date.

Subject-level end of study (EOS) date

The EOS date for each subject is defined as the last date on which the subject participated in the study. The date will be recorded on the Disposition electronic case report form (eCRF) page.

2.1.1.2 Visit and analysis window

Since the actual visit for a subject may not exactly coincide with their targeted visit date, the actual visit date is mapped to a study visit.

The nearest study day window will be utilized to define study visit for laboratory, vital signs, number of doses received, ophthalmological assessments and GO-QoL collected during office visits before dose is administered.

In case of multiple assessments within an analysis window, the day the closest to the scheduled visit day will be used.

Unscheduled visits will only be used when there is no measurement from the scheduled visit in the defined window. In case of multiple assessment values among the same type of visit (i.e., scheduled vs. unscheduled) within the same analysis window, the closest to the scheduled visit

day will be used. In case of equal distances (e.g., same day), the latest assessment value will be used.

For assessments that are not scheduled at all visits (e.g. hematology assessments) the derivation formula is:

- Lower limit = upper limit of previous visit +1.
- Upper limit = integer value of (target day + target day of next visit)/2.

Table 2-1 Study visit windows during DBTP

Study visit	Target day	Study day
DBTP		
Baseline	1	≤1
Week 1	8	2 – 11
Week 2	15	12 – 18
Week 3	22	19 – 25
Week 4	29	26 – 43
Week 8	57	44 – 71
Week 12	85	72 – 99
Week 16	113	100 – 127

Table 2-2 Study visit windows during open-label treatment and follow-up for non-responders

Study visit	Target day	Study day
Week NR 16*	113	100 – 116
Week NR 17	120	117 – 123
Week NR 18	127	124 – 130
Week NR 19	134	131 – 137
Week NR 20	141	138 – 155
Week NR 24	169	156 – 183
Week NR 28	197	184 – 211
Week NR 32	225	212 – 253
Week NR 40	281	254 – 337
Week NR 56	393	338 – 448

*Only applicable for assessments that have not been performed at Week 16 visit in non-responders.

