### Table 8-2 Assessment schedule (re-treatment for non-responders and relapsers)

Period	Second C	ourse Trea	tment Perio	d					Post-Trea	w-Up	
Visit name non-responder	Week NR16 	Week NR17	Week NR18	Week NR19	Week NR20	Week NR24	Week NR28	Week NR32	Week NR40	Week NR56	USV 
Days	113	120	127	134	141	169	197	225	281	393	
Visit name relapsers§	Week R0 	Week R1	Week R2	Week R3	Week R4	Week R8	Week R12	Week R16	Week R24	Week R40	USV 
Days since relapse	1	8	15	22	29	57	85	113	169	281	
Physical examination	S					S		S	S		(S)
Ophthalmologic assessment 	Х		Х		х	Х	х	х	Х	х	(X)
Weight	Х							Х			
Vital signs	Х	Х	Х	х	Х	Х	Х	х	Х	х	(X)
Hematology and blood chemistry (fasting)	Х				х	Х	х	х	х		(X)
Urinalysis (local analysis) 	S							S	S		(S)
Thyroid laboratory assessments (fasting)	Х				Х	Х	Х	Х	Х	Х	(X)
Urine pregnancy test (local analysis)	S				S	S	S	S	S	S	(S)
Adverse events (including injections site reactions)	Х	Х	Х	Х	Х	Х	Х	Х	x	Х	Х
Responder/NR-assessment								Х			
Prior/concomitant medications/non-drug therapy			1	1	Upd	ate as neces	ssary	1		1	
	V		V		V	V	v	V	v	v	(X)
CAS	Х		Х		Х	Х	Х	Х	Х	Х	(X)

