2.4 Treatments (study treatment, rescue medication, concomitant therapies, compliance)

2.4.1 Study treatment / compliance

Descriptive statistics for exposure to study treatment will be provided based on the SAF.

The duration of exposure to study treatment will be summarized by treatment group.

In addition, the number of treatment syringes will be presented by treatment group in frequency tables by visit and cumulatively.

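### SAP Table 2-2 assigns open-label doses to windows fixed from study Day 1, so a second course starting four or more days off Day 113 can be misplaced in the by-visit syringe table

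*SAP*

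**What the plan says.** SAP 2.1.1.2 maps actual dates to study visits: "The nearest study day window will be utilized to define study visit for laboratory, vital signs, number of doses received", followed by ophthalmological assessments and GO-QoL. When several records compete, "In case of multiple assessments within an analysis window, the day the closest to the scheduled visit day will be used". For items not scheduled at every visit, windows come from a midpoint rule: "Upper limit = integer value of (target day + target day of next visit)/2", with each lower limit one day after the previous upper limit.

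Table 2-1 accepts the double-blind Week 16 visit over four weeks: "Week 16 113 100 – 127". Table 2-2 gives the open-label windows for non-responders on the same Day 1 scale. Its first row is "Week NR 16* 113 100 – 116"; seven-day windows follow for NR17 to NR19, then "Week NR 20 141 138 – 155". A footnote limits the NR16 row to assessments not already done at Week 16.

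SAP 2.4.1 states the output that uses dose counts: "the number of treatment syringes will be presented by treatment group in frequency tables by visit and cumulatively".

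**The concern.** The open-label course begins when the patient attends Week 16, but its windows do not move with that visit. A Week 16 visit with a first open-label dose on Days 117 to 127 is Week 16 in Table 2-1 and NR17 or NR18 in Table 2-2. Because the loading windows are only seven days wide, a modest shift moves several weekly doses into neighbouring windows.

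At stake is the syringe table. A patient who received all seven doses could appear to have missed one visit and received two or three doses at another. The SAP does not say whether doses sharing a window are summed or reduced to one, so the cumulative count is also open to doubt.

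**Working it through.** **Inputs.** Table 2-2 limits (SAP 2.1.1.2). Target days 113, 120, 127, 134, 141, 169, 197, 225, 281, 393 (protocol Table 8-2, non-responder row). Seven doses at Weeks 16, 17, 18, 19, 20, 24 and 28 (SAP 2.1.1), which are offsets of 0, 7, 14, 21, 28, 56 and 84 days. Possible starts: Days 100 to 127 (Table 2-1).

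**Reproducing Table 2-2.** Upper limit = int((target + next target)/2):
- (113+120)/2 = 116.5, giving 116
- (120+127)/2 = 123.5, giving 123; likewise 130 and 137
- (141+169)/2 = 155; likewise 183, 211, 253 and 337

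All agree with the table. The first lower limit (100) and the last upper limit (448) are taken as printed.

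**Case 1: spacing kept from the first open-label dose.** A start on Day 117 gives doses on Days 117, 124, 131, 138, 145, 173 and 201. For every start:

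| First dose (day) | Windows of the seven doses | Wrong label | Crowded window |
|---|---|---|---|
| 100–102 | NR16, NR16, NR16, NR17, NR18, NR24, NR28 | 4 | 3 in NR16 |
| 103–109 | NR16, NR16, NR17, NR18, NR19, NR24, NR28 | 4 | 2 in NR16 |
| 110–116 | as planned | 0 | none |
| 117–123 | NR17, NR18, NR19, NR20, NR20, NR24, NR28 | 4 | 2 in NR20 |
| 124–127 | NR18, NR19, NR20, NR20, NR20, NR24, NR28 | 4 | 3 in NR20 |

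Starts 15 to 21 days late lie outside the Week 16 window; there all seven dosing visits would be mislabelled.

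**Case 2: return to the designated days.** After a start on Days 117 to 119 (4 to 6 days late), the next doses fall on Days 120, 127, 134 and 141. The first is labelled NR17 and shares that window with the second: one wrong label, two doses in one window, NR16 empty. An early start stays in NR16 and the rest map correctly.

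**Cumulative count.** If doses are summed, the total stays at 7 (14 syringes at two per dose). If the closest-record rule is applied to doses, it becomes 6 (12 syringes) with one surplus dose or 5 (10 syringes) with two.

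**Other items, using the midpoint rule on their own schedules, with spacing kept.**
- CAS, proptosis and GO-QoL at NR16, NR18 and NR20: (113+127)/2 = 120, (127+141)/2 = 134 and (141+169)/2 = 155 give windows 100–120, 121–134 and 135–155. Labels change only for starts 8 or more days late or 7 or more early, at two visits. With a start on Day 121, the NR18 assessment (Day 135) is 6 days from the NR20 target of 141 and the true NR20 assessment (Day 149) is 8 days away, so the closest-day rule keeps the wrong one.
- Haematology and chemistry at NR16 and NR20: (113+141)/2 = 127 gives windows 100–127 and 128–155. No start on Days 100 to 127 shifts a label.

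**The case against.** Four arguments limit the point.

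1. *Doses are not shown to be lost.* A reader might infer that one or two of the seven doses disappear from the analysis. The closest-record rule speaks of assessments and never names doses, and every dose is on the Dosage Administration Record CRF (protocol 6.6.1). Loss follows only if a programmer extends the rule to doses. This objection stands. The wrong by-visit label does not depend on it.

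2. *Spacing is not settled.* Protocol section 8 asks for visits as close as possible to the designated day, while section 4.2 describes weekly loading for the second course. Neither says what happens after an early or late start. This also stands: four wrong labels is a conditional result. For late starts the defect survives in smaller form under the other reading.

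3. *Table 2-2 follows the protocol.* Its targets equal the non-responder days in protocol Table 8-2. That table counts relapsers by "Days since relapse", but relapse can occur at any time up to Week 68, so fixed study days were never possible for them. The contrast does not show that the protocol recognised and avoided an error.

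4. *Re-anchoring can do harm.* With targets 1, 8, 15, 22, 29 and 57, the midpoint rule gives upper limits 4, 11, 18, 25 and 43. A start on Day 118 with a return to Days 120, 127, 134 and 141 gives relative days 1, 3, 10, 17 and 24. Four visits are then mislabelled, against one under Table 2-2. Re-anchoring is therefore right only if doses were in fact spaced from the first open-label dose.

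**Conclusion.** The point holds in a limited form. Applying Table 2-2 to dose counts gives a wrong by-visit syringe table for starts 4 to 14 days late or 4 to 13 days early if spacing is kept, and for starts 4 to 6 days late if patients return to the designated days. Starts within three days of Day 113 are safe under either assumption. The cumulative count is at risk only because the SAP does not say how doses sharing a window are handled.

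A reader might infer that exposure, vital signs or efficacy conclusions are also distorted. The documents do not support that:
- Exposure duration is computed from dates (SAP 2.1.1.5), and AE incidence does not use Table 2-2.
- Week 16 endpoints use Table 2-1.
- The vital-signs display is a frequency table of notable values by period, not by visit (SAP 2.8.4.2).
- Only by-visit open-label efficacy and GO-QoL summaries (SAP 2.6.2 and 2.11) can be affected, at two visits and at larger shifts. For late starts one of these is NR16 itself, which the footnote restricts to assessments not done at Week 16.

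SAP section 1 gives 23 patients in follow-up. How many took open-label drug, and on which days they started, is not stated, so the number affected cannot be estimated. In a terminated trial with purely descriptive analysis the severity is minor.

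**What to change.** In SAP 2.1.1.2, remove the dose count from the list of windowed items. In SAP 2.4.1, state that syringes are counted from the dosing record by nominal visit, that all doses are summed and that none is discarded. This is correct under either spacing assumption, provided the dosing record carries the visit label.

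For other open-label by-visit summaries, use the nominal NR visit for scheduled visits and keep day windows for unscheduled assessments only. Alternatively, anchor the Table 2-2 windows to the first open-label dose, but only after confirming from the dosing dates that the course was spaced from that dose.

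The cost is a short text change and a small change to derivation programs. No new data are needed.

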#### Novartis Amended Protocol (Version No. 02Track Changes)

#### Page 58 of 99 Protocol No. CAIN457ADE16

Period	Second C	Second Course Treatment Period				Post-Treatment Follow-Up					
Visit name non-responder	Week NR16 	Week NR17	Week NR18	Week NR19	Week NR20	Week NR24	Week NR28	Week NR32	Week NR40	Week NR56	USV 
Days	113	120	127	134	141	169	197	225	281	393	
Visit name relapsers§	Week R0 	Week R1	Week R2	Week R3	Week R4	Week R8	Week R12	Week R16	Week R24	Week R40	USV 
Days since relapse	1	8	15	22	29	57	85	113	169	281	
Proptosis measurement	Х		Х		Х	Х	Х	Х	Х	Х	(X)
Diplopia grading 	Х		Х		Х	Х	х	Х	х	Х	(X)
GO-QoL	Х		Х		х	х	х	Х	Х	х	
Contact Interactive Response Technology (IRT)	х	Х	Х	х	х	х	х	х			
Study drug administration*	Х	Х	Х	Х	Х	Х	Х				

Confidential

\* = Patients who are non-responders at Week 16 or patients who relapse during follow-up receive 16 weeks of treatment with open-label secukinumab.

§ = Relapse can occur at any time during the 52-week follow-up period (i.e., from Week 16 onward to Week 68).

X = assessment to be recorded in the clinical database or received electronically from a vendor. S = source data.

1 = Ophthalmic examination (please refer to Section 8.3.4).

2 = Unscheduled visits (USV) might be required e.g., if patients observe symptoms between scheduled visits or for safety reasons. The safety assessments listed herein may be performed at the discretion of the investigator as needed to resolve the reason for the unscheduled visit. (S)AE assessment and concomitant medications are mandatory for all unscheduled visits.

3 = Kits for urinalysis will be provided by central lab and test is performed locally.

4 = Only applicable for assessments that have not been performed at the W16 Visit in non-responders.

5 = Only applicable for assessments that have not been performed at the Visit at which relapse was diagnosed.

6 = Gorman score/subjective diplopia score (Bahn et al 1987).

() = Parentheses denote assessments that are on a per need basis at investigator's discretion.

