2.8 Safety analyses

Summaries may be performed separately for initial (Baseline to Week 16) period and entire study period (including follow-up). Week 16 is chosen due to the fact that patients may be switched to another treatment at this time. Use of data up to and including the last visit before first switch opportunity provides an unbiased comparison between AIN and placebo; data collected beyond Week 16 are included in analyses which summarize the entire study period.

All listings and tables will be presented by treatment group. Safety summaries include only data from the on-treatment period and follow-up period with the exception of Baseline data that will also be summarized where appropriate (e.g., change from Baseline summaries). The on-treatment period is defined as date of first treatment to (date of last treatment + 84 days).

In addition, a separate summary for death including on-treatment and post-treatment deaths will be provided.

In particular, summary tables for AEs will summarize only on-treatment events, with a start date during the on-treatment period (treatment-emergent AEs) for the DBTP and the entire study period.

Missing data will not be imputed for safety endpoints.

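### Can an NR18 value taken on open-label secukinumab enter the Week 16 efficacy summary because the SAP's visit windows overlap?

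*SAP*

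**What the plan says.** SAP 2.1.1.2 maps actual visit dates to study visits through two tables. Table 2-1, captioned "Study visit windows during DBTP", gives Week 16 (target Day 113) as Days 100–127. Table 2-2, captioned for open-label treatment and follow-up in non-responders, gives NR16 as 100–116, NR17 as 117–123 and NR18 as 124–130.

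The mapping step assigns a visit by the nearest study day window. Only then do the selection rules apply: "In case of multiple assessments within an analysis window, the day the closest to the scheduled visit day will be used", and "In case of equal distances (e.g., same day), the latest assessment value will be used". For assessments not scheduled at every visit, the section adds a formula: "Upper limit = integer value of (target day + target day of next visit)/2".

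Open-label doses come before NR18: "Non-responders at Week 16: Secukinumab (300 mg) at Week 16, Week 17, Week 18" (SAP 2.1.1). Protocol Table 8-2 schedules CAS, proptosis, diplopia and GO-QoL at NR16, NR18 and NR20 but not at NR17, and its NR16 footnote reads "Only applicable for assessments that have not been performed at the W16 Visit in non-responders".

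A pre-switch principle is stated for safety in SAP 2.8: "Use of data up to and including the last visit before first switch opportunity provides an unbiased comparison between AIN and placebo". The efficacy sections have no counterpart.

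**The concern.** Days 117–127 belong to two windows, and no sentence says which table takes precedence once a patient has started open-label drug. If Table 2-1 is applied to every assessment by date alone, an NR18 value can be reported as Week 16 in two situations:

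- **Case 1:** the item is missing at Week 16 and at the NR16 catch-up, so NR18 is the only value in the window.
- **Case 2:** the Week 16 visit was so early that NR18 lies as close to Day 113, or closer.

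For a patient randomized to placebo, that value would have been taken on secukinumab. It would blur the Week 16 contrast, the one time point at which the arms can be compared before switching.

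**Working it through.** **Inputs.** Target days: Week 16 = 113, Week 20 = 141 (Protocol Table 8-1); NR16 = 113, NR17 = 120, NR18 = 127, NR19 = 134 (Protocol Table 8-2). Windows and rules are from SAP 2.1.1.2.

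**1. The printed limits reproduce.** With upper limit = integer part of (target + next target)/2:
- Week 16: (113 + 141)/2 = 127
- NR16: (113 + 120)/2 = 116.5, giving 116
- NR17: (120 + 127)/2 = 123.5, giving 123
- NR18: (127 + 134)/2 = 130.5, giving 130

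The overlap of 100–127 with 117–130 is Days 117–127. The part in NR17 (117–123) carries no scheduled efficacy data.

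**2. On-time visits.** With Week 16 on Day 113 and NR18 on Day 127, the distances from Day 113 are 0 and 14. The Week 16 value is kept.

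**3. Literal reading of the selection rules.** Let D be the Week 16 day and E the NR18 day, with E after Day 113.
- Case 1: any E up to 127 is inside the Week 16 window, including an on-time Day 127.
- Case 2: NR18 is chosen when E − 113 ≤ 113 − D, that is D + E ≤ 226. With E in its printed window (124–130) and no later than 127, the pairs (D, E) are (100,124), (101,124), (102,124), (100,125), (101,125) and (100,126): six pairs. At the scheduled E = 127, D would have to be 99 or less, which is outside the window.

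**4. Apply the mapping step first.** Compare the distance to the NR18 target, 127 − E, with the distance to the Week 16 target, E − 113. They are equal at E = 120.
- For E = 124 to 127, the distances are 3 to 0 days from NR18 against 11 to 14 from Week 16. Each visit maps to NR18. This removes the on-time part of case 1 and all six pairs of case 2.
- The SAP formula, applied to the non-responder efficacy schedule (Week 16, then NR18), gives the same boundary: (113 + 127)/2 = 120. NR18 would start at Day 121, with no overlap.

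**5. What is left.** E must be 120 or earlier, at least 127 − 120 = 7 days ahead of schedule. If NR18 is held 14 days after the actual Week 16 visit (an assumption), then 2D + 14 ≤ 226 gives D ≤ 106. That means Week 16 on Days 100–106 and NR18 on Days 114–120. Protocol Table 8-2 sets non-responder visits by study day and counts only relapser visits from an event, so this spacing departs from the schedule.

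**6. Apply the period split.** SAP 1.1 runs the double-blind period from Baseline to Week 16. SAP 2.1.1.5 ends double-blind exposure for completers at the Week 16 visit date. SAP 2.3.1 defines completion of the period by completion of visits through the Week 16 assessments. An NR18 assessment follows that visit, so Table 2-2 governs it whatever its date. This removes the remainder in step 5.

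**7. Primary endpoint.** Overall response needs a proptosis reduction of at least 2 mm. Open-label drug is offered at Week 16 only to proptosis non-responders, identified at the assessment scheduled there. A switched patient should therefore already have a Week 16 proptosis result that rules out overall response, whatever the CAS. Case 1 cannot change this. Case 2 could touch it only if the recorded Week 16 proptosis were overridden by a later on-drug value.

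**The case for a change.** The best argument for acting is that the separation is inferred. The captions name periods, but the study-dates section defines neither an end date for the double-blind period nor a first open-label dose date. The definitions in step 6 are exposure and disposition rules, not mapping rules. The tables are not disjoint by design, since Week 16 and NR16 already share Days 100–116. The SAP's remark that assessments precede dosing refers to the dose at the same visit, so it does not exclude NR18. The protocol gives no numeric visit window, so a site that held Week 16 early might well count weekly doses from there. Capping the window would not help either: with a Day 116 cap and 14-day spacing, Week 16 on Days 100–102 would still lose to NR18 on Days 114–116. With 28 randomized, about 14 per arm if allocation was even (an assumption), one altered response status moves a proportion by 1/14, about 7 percentage points. The SAP reports no responders, so most of the 23 patients in follow-up may be on the Table 2-2 schedule.

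It stands that no sentence states the rule for efficacy. It does not follow that the plan yields wrong summaries. An analyst with two tables captioned by period, recorded dose dates and a pre-switch principle in the safety section would not assign a visit made after two open-label doses to the double-blind period. The 7-point figure also requires a changed response status, which step 7 makes remote for the primary endpoint. CAS response, diplopia response, mean changes and GO-QoL could in principle be touched, but only through the rare timing in step 5.

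**Conclusion.** No change to the plan follows. The printed ranges do overlap on Days 117–127, but this is a gap in wording that analysts fill sensibly. The captions and the double-blind period definitions separate the two schedules, and nearest-day mapping alone sends any NR18 visit on Days 124–127 to NR18. Without the period split, a post-switch value could enter the Week 16 summary only if NR18 took place on about Day 120 or earlier and, in addition, the Week 16 item was missing or the Week 16 visit was very early (Days 100–106 under 14-day spacing). The documents do not allow a count of such patients, and it may be zero.

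The conclusion rests on two assumptions: that the captions are read as assigning each table to its period, and that open-label entry followed a recorded Week 16 proptosis non-response, as the protocol requires. Under these, the primary endpoint is essentially unaffected. The remaining summaries carry no tests in this terminated 28-patient study, and following the plan as written would still give sound results.
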